# 7.6. Subject Withdrawal Criteria

Each subject may withdraw consent at any time during the study without penalty. Counseling about the subject's health will be provided if he or she decides to discontinue participation in the study. Medical advice regarding what is in the best interest of the subject will be provided.

The PI may discontinue the subject's activity without the subject's consent if any of these criteria are met:

- A subject fails to comply with study procedures;
- A subject's safety or health may be compromised by further participation; or
- A subject's Primary Care Physician wishes to withdraw the subject.

### 7.6.1. When and How to Withdraw Subjects

A subject may end his or her participation in the study at any time. If a subject withdraws, the PI will make a reasonable effort to determine the reason for the withdrawal from the study and to complete termination procedures as described in section 8.4. Telephone calls, registered letters, and email correspondence are considered reasonable effort. A minimum of 2 documented attempts to contact the subject should be made over the course of 1 week. If the site personnel receive no response, they should send a registered letter requesting that the subject contact the site regarding his or her status in the study. If the subject does not respond at this point, the date the certified letter was mailed will be considered the date of study withdrawal. For subjects leaving the study, a targeted examination may be performed, if medically indicated and if permitted by the subject.

A subject may be withdrawn for an AE or SAE resulting in a safety concern or for noncompliance with protocol requirements. When a subject withdraws due to an AE or is withdrawn by the PI due to an AE, the PVG MD, the sponsor's safety office (USAMRMC USAMMDA ORA) must be notified within 72 hours ([contact]). The PI must follow specific policies regarding the timely reporting of AEs and SAEs to the local IRB (section 10.6.2). In all cases, the PI will make a reasonable effort to complete study termination procedures.

If a subject meets the withdrawal conditions for a concomitant medication violation or noncompliance, this should clearly be stated in the source document and the study termination eCRF.

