#### 6. TRIAL OBJECTIVES AND PURPOSE

## 6.1. Primary Objective

The primary objective of this study is to assess the safety of single infusions with the RePlasTM FDP product at increasing fixed doses of either 1 unit (approximately 270 mL), 2 units (approximately 540 mL), or 3 units (approximately 810 mL) in normal healthy subjects. In the 2 lower dose cohorts, safety will also be assessed in terms of the type of autologous plasma used as the starting material in the manufacture of the investigational product:

- FDP derived from WB where CPD was used as the anticoagulant, or FDP-CPD; and
- FDP collected by plasmapheresis where ACD was used as the anticoagulant, or FDP-ACD.

The highest dose cohort will receive FDP manufactured only from FFP collected by plasmapheresis (FDP-ACD). Conclusions on whether the study meets its safety objectives will be based only on treatment emergent adverse events (TEAEs). These are adverse events (AEs) that occur after treatment (plasma infusion) has begun and throughout the study's post-infusion follow-up period.

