### 7.6.2. Data Collected for Withdrawn Subjects

If a subject is withdrawn, all data collected up to the time of withdrawal will be reported. Ongoing AEs should be followed to resolution or stabilization, if the subject consents to passive review of his or her medical record. The study termination eCRF will be completed, with the reason for withdrawal specified.

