# 7.6.4. Follow-Up for Withdrawn Subjects

Subjects who are withdrawn from the study will be followed to satisfactory resolution of any ongoing AEs (or until the PI deems the event to be chronic/stable) at the time of withdrawal by passive observation and recording of the subject's medical record, if the subject consents to this process.

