### 8.3.4. 28-Day Follow-Up Visit

A post-infusion follow-up visit will be scheduled 28 days ( $\pm$  1 day) post-infusion for subjects enrolled in Cohorts 1 and 2. For subjects enrolled in Cohort 3, a 28-day post-infusion follow-up visit will take place after the second plasma infusion, only, approximately 42 days after the first infusion visit. The following procedures will be performed at these follow-up visits:

- Review of medical history, concomitant medications, and AEs since the 14-day telephone follow-up contact;
- Abbreviated physical exam which includes vital signs (blood pressure, heart rate, respiration rate, and temperature) and a general assessment of health;
- Collect blood samples as noted for all tests listed in the Schedule of Events tables (Table 4, Table 5, Table 6, and Table 8); and
- Exit interview concluding the subject's study participation.

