4.2.2 Safety Populations

The three subject populations for assessing safety are defined as those who:

- Receive any volume of infused product; (i.e., In Cohort 3 subjects this includes those who received a partial dose at either Infusion Visit) (**S1**);
- Receive the full infusion dose and have at least one outcome measure (**S2**); and
- Receive the full infusion dose and can be fully evaluated because in: (**S3**, or the per protocol population).
 - Cohorts 1 and 2 the subjects also minimally completed the 7-day follow-up visit; and

- Cohort 3 the subjects had both complete infusion doses and minimally completed the 7-day follow-up visit after the second infusion.

The demographic tables (Table 1.1- Table 1.20) will include all five analysis populations listed in Section 4.2 unless it is found that both full populations include the same subjects, in which case only one table for the F1 and F2 population will be produced with the title indicating that it represents the F1, F2 populations, unless otherwise specified. Likewise, if all three safety populations are found to include the same subjects, only one table will be produced with the title indicating that it represents all safety populations, the S1, S2 and S3, unless otherwise specified. This pattern of table reduction will be repeated for the remaining tables unless otherwise indicated. Subject disposition tables will include all five populations. AE tables that display overall AE incidence will include all five populations. Tables that are restricted to TEAEs will include the safety populations only. Study drug exposure will be presented in the first safety population (S1). All other analyses will be performed in the third safety population only (S3).

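### The protocol does not separate stopping study infusions from leaving the study, so new TEAEs and SAEs can go unsought in infused subjects who still count in full in S1

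*Protocol*

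**What the plan says.** - **Period of interest.** Protocol 6.1 rests the safety conclusion on TEAEs, which run from the start of infusion and "throughout the study's post-infusion follow-up period". The last scheduled visit is 28 days after infusion in Cohorts 1 and 2 (Day 29), and 28 days after infusion 2 in Cohort 3 (Day 43).
- **Withdrawal.** Protocol 7.6: "The PI may discontinue the subject's activity without the subject's consent if any of these criteria are met". The grounds are noncompliance, a threat to the subject's safety or health, or the wish of the primary care physician. Section 7.6.1 adds: "A subject may be withdrawn for an AE or SAE resulting in a safety concern or for noncompliance with protocol requirements".
- **After withdrawal.** Protocol 7.6.2: "If a subject is withdrawn, all data collected up to the time of withdrawal will be reported". Protocol 7.6.4: "Subjects who are withdrawn from the study will be followed to satisfactory resolution of any ongoing AEs", and this is done "by passive observation and recording of the subject's medical record, if the subject consents to this process".
- **Active elements that remain.** Section 8.4 requests an Early Discontinuation Visit (AE review, examination, laboratory tests) from a subject who leaves after the infusion and before the 7-day visit. Section 7.6.1 asks for a reasonable effort to complete termination procedures. Section 10.5.2 requires SAEs to be followed to resolution and has a related SAE reported whenever it comes to the investigator's notice. It does not oblige investigators to look for SAEs in former subjects.
- **Cohort 3.** Under Protocol 8.3.4, "a 28-day post-infusion follow-up visit will take place after the second plasma infusion, only". Section 8.3.2 has no 14-day call after infusion 1.
- **Analysis.** SAP 4.2.2 defines S1 as those who "Receive any volume of infused product". The footnotes to the SAP's TEAE tables take the treatment group N as the denominator.

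**The concern.** Once a subject has received product, the period at risk for a TEAE is set by that exposure, not by whether more product is given. A subject who reacts and is withdrawn is still at risk, but the plan stops looking for new events. Observation then ends early because of the outcome, and S1 percentages treat the subject as observed throughout.

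What is exposed is the set of events that first occur or worsen after withdrawal: SAEs, SUSARs, deaths, new preferred terms and maximum severity. These matter in a first-in-human study with 4 subjects per arm, where one event moves an arm's percentage by 25 points. The plan itself allows for delayed effects: Protocol 11.1.1 mentions that an event after the second infusion, such as an immunogenic response, may belong to the first.

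**Working it through.** **1. The plan's own figure.** Protocol Table 16 and SAP Table 3 give 1.6-29.2% (width 27.6) for 10% incidence in 24 subjects. A Clopper-Pearson interval with x = 0.10 × 24 = 2.4 returns the same values, and all nine cells reproduce. No printed figure is wrong. The table assumes that each of the n subjects is observed for the outcome.

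**2. Cohort 3 without infusion 2.** Scheduled post-infusion contacts anchored to infusion 1:

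| Contact | Anchored to infusion 1? | Study day |
|---|---|---|
| 24-hour visit | yes | 2 |
| 48- and 72-hour calls | yes | 3, 4 |
| 7-day visit | yes | 8 |
| 14-day call | no, infusion 2 only (8.3.2) | 29 |
| 28-day visit | no, infusion 2 only (8.3.4) | 43 |

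After Day 8 no post-infusion contact is tied to infusion 1. If the infusion is withheld at the Day 15 visit itself (8.2.2), the pre-infusion AE review may still take place, but nothing anchored to infusion 1 follows it. If there is no Day 15 attendance, 7 of the 14 days over which 11.1.1 attributes AEs to the latest product have no scheduled contact (Day 8 to Day 15).

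**3. Loss for one withdrawn subject.** Share of a 28-day period lost = (28 − d)/28, where d is days from infusion to withdrawal.
- d = 1: 27/28 = 96.4%
- d = 7: 21/28 = 75.0%

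One such subject in a Cohort 1 or 2 arm of 4 takes 27/112 = 24.1% or 21/112 = 18.8% of that arm's follow-up.

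**4. Study-wide illustration.** The documents give no rate of withdrawal after infusion, so 1, 2 or 4 of 24 are assumptions. Planned time is 16 × 28 + 8 × 42 = 784 subject-days. Loss is k × (28 − d)/784 in Cohorts 1 and 2. In Cohort 3, with d counted from infusion 1, it is k × (42 − d)/784.

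| Withdrawn, k | All in Cohorts 1-2, d = 1 | d = 7 | All in Cohort 3, d = 1 | d = 7 |
|---|---|---|---|---|
| 1 | 3.4% | 2.7% | 5.2% | 4.5% |
| 2 | 6.9% | 5.4% | 10.5% | 8.9% |
| 4 | 13.8% | 10.7% | 20.9% | 17.9% |

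**5. Effect on a reported SAE percentage.** Let q be the chance of a new SAE after withdrawal, and suppose none comes to light. The understatement on N = 24 is k × q/24. For q from 10% to 50% (assumed):
- k = 1: 0.4 to 2.1 points
- k = 2: 0.8 to 4.2 points
- k = 4: 1.7 to 8.3 points

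These are upper limits for each q, since some events would be learned of anyway. N = 24 is also a simplification: 7.6.3 replaces subjects who discontinue, so S1 may exceed 24. One missed SAE turns 1/24 (95% CI 0.1-21.1%) into 0/24 (0-14.2%).

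**6. What does not move.** SAP TEAE tables count a subject at most once per row. A subject withdrawn for a TEAE is already in the any-TEAE row.

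**The case against.** The case for leaving the text alone has real substance.

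- **Withdrawal is optional.** Sections 7.6 and 7.6.1 say may. A reader might infer that stopping an infusion means leaving the study, but no section says so. Section 8.2 lets the investigator withhold an infusion without calling it withdrawal, and the SAP tabulates AEs leading to treatment discontinuation apart from study completion. SAP 4.5.2 does class a Cohort 3 subject without infusion 2 as discontinued, but that defines a flow-diagram box and does not end follow-up. This stands. What remains is that nothing says such a subject stays on schedule.
- **Follow-up is not purely passive.** A reader of 7.6.4 alone might think so. The Early Discontinuation Visit and the duty to follow SAEs contradict it. But that visit is one contact, requested only before the 7-day visit, and following known SAEs does not find new ones.
- **Late laboratory results are not biased in S1.** It is tempting to add PT/INR, aPTT and DAT to the list of exposed outcomes. SAP 4.2.2 runs the laboratory tables in S3 only, so that extension fails.
- **S3 does not drop all these subjects.** A Cohort 1 or 2 subject who received the full dose and leaves after the 7-day visit is a completer under 7.6.3 and stays in S3.
- **Scope.** Sixteen of 24 subjects have a single infusion, so once it is complete there is no treatment left to stop. For them only the withdrawal rules matter.
- **The calendar could be read as continuing.** Section 6.8 lists Cohort 3 contacts by study day up to Day 43. But 8.3.2 and 8.3.4 define the late ones by infusion 2, and neither says what happens without it.

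**Conclusion.** The point holds as a gap in safety data collection. Under the stated rules, an infused subject who is withdrawn has no active search for new TEAEs or SAEs beyond at most the termination procedures. A Cohort 3 subject without infusion 2 has no post-infusion contact tied to infusion 1 after Day 8. S1 percentages make no allowance for either.

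The size cannot be determined, because the documents give no withdrawal rate and no expected timing of later events. The losses above (2.7% to 20.9% of planned follow-up time; 0.4 to 8.3 points on an SAE percentage) are illustrations under assumed inputs. The n = 20 row of Table 16 is included for general attrition and comparison, and should not be read as a forecast of withdrawals for AEs.

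Two stronger readings are not supported. The overall TEAE incidence is not lowered for a subject withdrawn for a TEAE. Nor do the documents show a bias in favour of FDP over FFP. Missed later events can only lower the counts, but in Cohort 3 withdrawal may follow either product, so the direction of the comparison is undetermined.

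This is worth correcting before enrollment, as a cheap improvement. It does not invalidate the design.

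**What to change.** - **Protocol 7.6.1 and 7.6.4.** Distinguish no further study infusion from withdrawal from the study. Ask every subject who received any volume of product to stay on the already scheduled safety contacts through 28 days after the last infusion actually received, unless the subject withdraws consent or participation is ended under the existing 7.6 grounds.
- **Protocol 8.3.2 and 8.3.4.** In Cohort 3, count the 14-day call and the 28-day visit from infusion 1 when infusion 2 is not given.
- **SAP 4.2.2 and 4.5.3.** Report the AEs so collected in S1, together with follow-up time by arm, so that a reader can see how completely each denominator was observed.

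The criteria for stopping an infusion or withdrawing a subject stay as they are; only data collection changes. The cost is a short amendment. A few subjects would attend contacts already in the schedule, with no new assessments. Some may decline, and would be handled as withdrawals of consent, as now.

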### 7.6.2. Data Collected for Withdrawn Subjects

If a subject is withdrawn, all data collected up to the time of withdrawal will be reported. Ongoing AEs should be followed to resolution or stabilization, if the subject consents to passive review of his or her medical record. The study termination eCRF will be completed, with the reason for withdrawal specified.

### 7.6.3. Replacement of Subjects

A total of 24 subjects (8 in each cohort) are to fully complete the trial. Depending on the cohort, study completion is defined as:

- Cohorts 1 and 2: infused with autologous FDP and completion of the 7-day post-infusion follow-up visit; and
- Cohort 3: infused with both the autologous experimental and control products per the assigned treatment sequence and completion of the 7-day post-infusion follow-up visit subsequent to the second infusion.

In cases where subjects discontinue participation prior to study completion, a replacement subject will be enrolled in the study. The replacement, assigned a new and unique SID, will be assigned to the same treatment arm as the discontinued subject. This is necessary to maintain the 1:1 subject ratio across study arms.

# 7.6.4. Follow-Up for Withdrawn Subjects

Subjects who are withdrawn from the study will be followed to satisfactory resolution of any ongoing AEs (or until the PI deems the event to be chronic/stable) at the time of withdrawal by passive observation and recording of the subject's medical record, if the subject consents to this process.

### 8. TREATMENT OF SUBJECTS

#### 8.1. Whole Blood and Plasma Collection

The purposeful use of plasmapheresis in this study, particularly for Cohort 3 subjects, provides practical advantages to subjects (eg, fewer required collection visits) and minimizes potential issues related to subject safety. WB donations generally provide a net volume of approximately 250 mL of derived plasma and typically require a 56-day interval between donations. In this study, subjects who are required to make more than one autologous WB donation (eg, subjects in Cohort 2, Arm 3), the donation interval will be abbreviated to 28 days. Plasmapheresis collections, in contrast, have a much shorter 7- to 10- day donation interval since there is minimal loss of red blood cells (RBCs) during the process. The volume that can be collected during single plasmapheresis is  $\leq 800$  mL, depending on the donor's size, which is over twice the plasma volume derived from WB donation. Limiting enrollment of subjects to those who weigh  $\geq$ 140 lbs and  $\leq$  220 lbs will help ensure each autologous plasmapheresis yields 600 mL to 800 mL plasma based on established volume limits for automated plasma collection (FDA-1992). Regardless of cohort or treatment arm, all subjects will have SPEP performed at each plasmapheresis collection. If any abnormalities are detected, subjects will be referred to a physician, scheduled for early withdrawal, and replaced with another subject. For subjects undergoing multiple plasmapheresis collections, total protein will be performed STAT or up to 24 hours prior to initiating the plasmapheresis. Total protein will only be performed at subsequent plasmapheresis sessions, not during the first collection. All subjects regardless of cohort or treatment arm will be provided with information and instructions regarding the use of iron supplements (see Appendix G) during the donation period.

Following standard blood product SOPs, subjects' plasma products collected, manufactured, and prepared for autologous infusion will be visually examined. The visual inspection of both FFP and reconstituted FDP will include observation for signs of lipemia, hemolysis, clotting, and macroscopic particulate matter. Plasma units that do not meet the visual examination criteria will be discarded per the site's SOP for the destruction of blood and blood products.

#### 8.1.1. Cohort 1 Blood and Plasma Collection

WB donors who are enrolled in the study will automatically be assigned to the FDP-CPD study arm of Cohort 1. Similarly, plasmapheresis donors who are enrolled will automatically be assigned to the FDP-ACD study arm of Cohort 1. Subjects in Treatment Arm 1 will receive a 1

unit (approximately 270 mL) transfusion of FDP manufactured from WB-derived plasma. Subjects in Treatment Arm 2 will receive a 1 unit (approximately 270 mL) transfusion of FDP manufactured from plasmapheresis. During the collection visit all subjects in Cohort 1 will:

- Be asked to provide information about medical history, concomitant medications, and AEs since the screening visit;
- Undergo an abbreviated physical exam which includes vital signs (blood pressure, heart rate, respiration rate, and temperature) and a general assessment of health;
- Complete the AABB Donor History Questionnaire; and
- Provide a sample of blood for hematocrit testing prior to donation per the SOPs in place at the site.

Treatment Arm 1 subjects will provide a single unit (approximately 500 mL) WB donation using the standard WB donation procedures in place at the site. Post-donation, subjects will be monitored for any adverse effects associated with WB donation (see section 5.6.1.2).

Treatment Arm 2 subjects will provide a single unit plasmapheresis donation (approximately 600 mL) using the standard plasmapheresis donation procedures in place at the site. Post-donation, subjects will be monitored for any adverse effects associated with plasmapheresis donation (see section 5.6.1.3).

If a subject has low hematocrit on the day of donation, they may, at the discretion of the investigator, be rescheduled for a second attempt at blood/plasma collection.

Subjects who provide low volume donations, <450 mL for Treatment Arm 1 and <500 mL for Treatment Arm 2, may, at the discretion of the investigator, be withdrawn from the study or rescheduled for a second attempt at blood/plasma collection. If, for example, the low volume donation occurs in a subject who enrolled early enough for a second donation attempt to be made within the scheduled time frame for the cohort, the subject will remain in the study and be given the opportunity for a second donation. Those subjects in Treatment Arm 2 who provide a low volume donation and who are scheduled for another attempt at the plasmapheresis collection will have another SPEP performed in addition to STAT total protein. All low-volume collections will be discarded by the clinical site following their SOP for handling blood and blood products.

#### 8.1.2. Cohort 2 Blood and Plasma Collection

Cohort 2 subjects will be assigned to 1 of the 2 treatment arms as described in section 6.6.1. Subjects in Treatment Arm 3 will receive a 2 unit (approximately 540 mL) transfusion of FDP manufactured from WB-derived plasma. Subjects in Treatment Arm 4 will receive a 2 unit (approximately 540 mL) transfusion of FDP manufactured from plasmapheresis. During collection visits all Cohort 2 subjects will:

- Be asked to provide information about medical history, concomitant medications, and AEs since the screening visit;
- Undergo an abbreviated physical exam which includes vital signs (blood pressure, heart rate, respiration rate, and temperature) and a general assessment of health;
- Complete the AABB Donor History Questionnaire; and

• Provide a sample of blood for hematocrit testing prior to (each) donation per the SOPs in place at the site.

Treatment Arm 3 subjects will provide a single unit (approximately 500 mL) WB donation using the standard WB donation procedures in place at the site. Post-donation, subjects will be monitored for any adverse effects associated with WB donation (see section 5.6.1.2). Due to the volume of plasma required to manufacture 2 units (approximately 540 mL, total) of FDP, Treatment Arm 3 subjects will be scheduled for a second WB donation session, no less than 28 days from the date of their first donation. Subjects in this arm who provide a low-volume donation (< 450 mL) may, at the discretion of the investigator, be withdrawn from the study or scheduled for a second donation attempt. The donation portion of each WB donation visit is expected to take no more than 1 hour. The procedures described above will be followed at both WB donation visits.

Treatment Arm 4 subjects will provide a single unit plasmapheresis donation (up to 800 mL) using the standard procedures in place at the site. Subjects will undergo SPEP, which will be measured during their plasmapheresis donation. Post-donation, subjects will be monitored for any adverse effects associated with plasmapheresis donation (see section 5.6.1.3). A second plasmapheresis donation visit should not be required for Treatment Arm 4 subjects. Subjects providing a low volume plasmapheresis donation (< 500 mL) may, at the discretion of the investigator, be withdrawn from the study or scheduled for a second donation attempt. If a subsequent visit is scheduled to collect the volume of plasma required to manufacture the 2 units (approximately 540 mL, total) of FDP, an additional visit may be scheduled no less than 7 days from the date of the first donation. SPEP and STAT Total Protein will both be performed at any subsequent collection visits as a condition of initiating plasmapheresis.

Following standard blood collection SOPs, subjects who present to a collection visit with a low hematocrit may, at the discretion of the PI, be rescheduled for a later blood/plasma collection.

All low-volume collections will be discarded by the clinical site following their SOP for handling blood and blood products.

